5.3 Statistical/Analytical issues

5.3.1 Calculation of PD data (intragastric pH)

All available data, except as described in 8. Addendum to SAP on handling of pH-metry data will be used in the statistical analysis. A subject who withdraws prior to the last planned visit in the study will be included in the analyses up to the time of discontinuation. No imputation of missing data will be performed.

The addendum attached to the SAP provides guidance on how to handle pH-metry recordings and data for analysis and reporting.

5.3.2 PK drug concentration data

Concentration results that are below the lower limit of quantification (LLOQ) will be identified as below limit of quantification or not quantifiable (NQ) by the Bioanalysis lab.

For the PK analysis and plots of data, values <LLOQ before the first observed concentration will be entered as zero and values <LLOQ at any other time point will be excluded from the analysis (i.e., handled as missing data). The handling of these values will be justified and documented. Not quantifiable samples will be treated as missing data. In plots, the method used for handling values <LLOQ will be described in a footnote.

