5.2.2 Calculation of PK Data

Individual and mean PK profiles for concentrations of linaprazan glurate and linaprazan will be plotted in Phoenix[®] WinNonlin[®] and reported for all subjects in the PK analysis sets. Mean concentration data will be plotted against scheduled (nominal) sampling times while individual concentration data will be plotted against actual sampling times.

PK concentration data

All individual PK concentrations will be presented in listings included in the appendices of the CSR. These data will be presented and analyzed with the same precision as the source data provided by the bioanalytical laboratory.

PK parameters

The derived parameters will be listed individually by subject and summarized by treatment using descriptive statistics. PK parameters and actual elapsed sample collection times will be rounded for reporting purposes in by-subject listings.

PK data will be presented by treatment using summary statistics with number of measurements, arithmetic mean, SD, as well as median, minimum and maximum values. For the PK parameters AUC_{inf} , AUC_{0-t} , partial AUCs, C_{max} , C_{aver} , C_{trough} , and C_{min} the geometric mean and geometric coefficient of variation (CV%) will also be presented. For the PK parameters T_{lag} and T_{max} , only the median, minimum, and maximum values will be presented. For the PK parameter R_{acc} and $AUC_{extrap\%}$, the geometric mean and CV% will also be presented. All data will be listed by treatment and subject.

Individual and mean linaprazan glurate and linaprazan plasma concentrations will be plotted against time for each dose group.

In export datasets, PK parameters will be provided with full precision, and will not be rounded. Descriptive statistics of PK parameter data will be calculated using full precision values and rounded for reporting purposes only.

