5.6 Pharmacokinetic Analyses

The PK analysis will be performed based on the PK analysis set. All PK analyses will be performed according to the actual treatment and dose received. Actual sampling time points relative to dosing will be used in the calculations. Pre-dose concentration values will be excluded from the NCA and set to 0.

The parameters to be determined in the study are presented in section 4.6. Parameters directly derived from the plasma concentration – time plot are not further described (i.e., C_{max} , C_{min} , t_{max} , C_{trough}), but all other calculations to be performed are described in detail below. Missing sample around the anticipated T_{max} may be flagged as "not accepted" upon decision by the Pharmacokineticist.

Estimation of the terminal elimination rate constant (λ_z)

The terminal elimination rate constant (λ_z) is calculated by log-linear regression of the terminal portion of the plasma concentration time profile. At least three observations will be used to estimate λ_z and the data points used in each estimation are indicated in the individual PK profiles. Data points for calculation of $T_{1/2}$ via λ_z are selected based on visual inspection of log-concentration-time plots of individual profiles and adjusted if needed. Any exclusion of data points in the terminal phase for this estimation should be clearly justified in the PK analysis log.

The adjusted R² should be considered in the selection of samples for calculation of λ_z and preferably exceed a value of 0.8. If λ_z cannot be reliably estimated, because of a low value of R², it will be flagged as "not accepted" and the associated parameters may be reported as "not determined". Use

of λ_z values obtained from data spanning less than three half-lives is permissible on the judgement of the Pharmacokineticist.

For subjects with insufficient PK data available leading to an extrapolated AUC (AUC_{extrap%}) exceeding 20%, the parameters depending on λ_z will not be reported. The % of extrapolated AUC will be presented for all subjects.

Area under the plasma concentration-time curves (AUCs)

The area under the plasma concentration-time curves (AUCs) are calculated using the linear up -log down method (i.e., linear trapezoidal rule is used when concentration data is increasing and the logarithmic trapezoidal rule is used when concentration data is decreasing) using uniform weighing.

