 AUC_{inf} is calculated based on the AUC_{0-t} (AUC from time of dosing to the time point of the last quantifiable plasma concentration) and then extrapolated to infinity using the concentration in the last quantifiable sample (C_{last}) and the estimated terminal elimination rate constant (λ_z), as follows:

 $AUC_{inf} = AUC_{0-t} + (C_{last}/\lambda_z)$

Accumulation ratio (R_{acc})

Accumulation index will be calculated for the observed accumulation ratio:

R_{acc} AUC = AUC_{tau} last dose / AUC_{tau} first dose

R_{acc} C_{max} = C_{max} last dose / C_{max} first dose

terminal half-life (T_{1/2}) The half-life is calculated by ln2/ λ_z .

```
Apparent total clearance (CL/F)
```

Total body clearance for extravascular administration, CL/F= Dose/AUC_{inf}, or CL/F= Dose/AUC_{tau} at steady state

Apparent volume of distribution (V/F)

Volume of distribution based on the terminal elimination phase, V/F =Dose/(λz^*AUC_{inf}), or V/F=Dose/(λz^*AUC_{tau}) at steady state

Average concentration during a dosing interval (C_{aver}) C_{aver} will be calculated for repeated dosing, as follows: $C_{aver} = AUC_{tau}/_{tau}$

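### The below-LLOQ rules give early samples two values, bias trough and late concentration summaries upward when some subjects are below LLOQ, and put no Day 1 limit on the pre-dose zero

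*SAP*

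**What the plan says.** SAP section 5.3.2 says that the laboratory will report results below LLOQ either as below the limit of quantification or as not quantifiable (NQ). Its rules for the PK analysis and plots depend on timing. Early in the profile, "values <LLOQ before the first observed concentration will be entered as zero". Every below-LLOQ sample after that point is treated differently: "values <LLOQ at any other time point will be excluded from the analysis (i.e., handled as missing data". The section adds, without exception, "Not quantifiable samples will be treated as missing data". It also promises that the handling will be justified and documented, and footnoted in plots.

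SAP section 5.6 adds "Pre-dose concentration values will be excluded from the NCA and set to 0", without naming a day or dose. It gives no further rule for parameters read directly from the concentration profile ("time plot are not further described (i.e., C_{max} , C_{min} , t_{max} , C_{trough"). AUC0-t is defined as the "AUC from time of dosing to the time point of the last quantifiable plasma concentration".

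SAP section 5.2.2 plots mean concentrations at nominal times and presents PK data with "summary statistics with number of measurements, arithmetic mean, SD, as well as median, minimum and maximum values". For Ctrough and Cmin, among others, "the geometric mean and geometric coefficient of variation (CV%) will also be presented". Ctrough is a primary endpoint (section 2.4) and Cmin a secondary one (section 2.5). Section 5.7.1 plots pH holding time ratio against AUC, Cmax and Cmin, and plots mean pH and mean linaprazan concentration together against time.

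**The concern.** There are three separate problems.

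1. An early below-LLOQ sample is zero under one sentence of section 5.3.2 and missing under another. A programmer cannot follow both.
2. Leaving out later below-LLOQ values removes only the lowest observations. That does no harm to an area that ends at the last quantifiable sample. It is not harmless when concentrations are averaged across subjects at a late time point, or when end-of-interval concentrations are summarised by group. A post-dose below-LLOQ value can also never be a subject's Cmin. In the two-axis plots, mean concentration would come from quantifiable subjects only, while mean pH does not depend on the LLOQ.
3. The pre-dose zero is natural before the first dose. The study also has Day 14 profiles, where a pre-dose concentration may well be quantifiable and is close in meaning to the trough.

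At stake are the summaries of a primary endpoint, the mean profiles, and the low-concentration end of the plots meant to show which exposure measure tracks acid control.

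**Working it through.** The SAP gives no LLOQ, no below-LLOQ rate and no concentration data, so there is no planned figure to reproduce. Parts 1 and 3 are mainly a comparison of texts. The sizes below rest on stated assumptions.

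**Part 1: early samples.** Section 5.3.2 makes NQ a label for below-LLOQ results. A below-LLOQ sample before the first observed concentration is therefore zero (timing rule) and missing (NQ sentence). As an illustration, assume samples at 0, 0.5 and 1 h, with the first quantifiable value C1 at 1 h and zero at dosing.
- 0.5 h sample entered as zero: area over 0–1 h = 0.5 × 0.5 × C1 = 0.25 C1.
- 0.5 h sample missing: area over 0–1 h = 0.5 × 1 × C1 = 0.50 C1.

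**Part 2: later samples.** Assume lognormal concentrations with geometric CV 40–80% and a share p below LLOQ of 10%, 25% or 40%. Let s = sqrt(ln(1 + CV²)), which is 0.3853 at 40% and 0.7033 at 80%. Let z be the normal quantile at p. After dropping the values below LLOQ, relative to the full distribution:
- geometric mean ratio = exp(s × φ(z)/(1 − p));
- median ratio = exp(s × z*), with z* the normal quantile at p + (1 − p)/2.

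| p | φ(z)/(1 − p) | z* | Geometric mean, CV 40% / 80% | Median, CV 40% / 80% |
|---|---|---|---|---|
| 10% | 0.1950 | 0.1257 | 1.078 / 1.147 | 1.050 / 1.092 |
| 25% | 0.4237 | 0.3186 | 1.177 / 1.347 | 1.131 / 1.251 |
| 40% | 0.6439 | 0.5244 | 1.282 / 1.573 | 1.224 / 1.446 |

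The geometric mean is thus 8–15%, 18–35% and 28–57% too high at the three shares, and the median 5–9%, 13–25% and 22–45%. In simulated groups of 12 (the planned group size) with exactly the 1, 3 or 5 lowest values removed, the geometric mean rises by 6–11%, 16–32% and 27–55%. If the below-LLOQ values are kept and ranked lowest, the median is unchanged at all three shares, because p stays below one half.

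Substituting LLOQ/2 shifts the geometric mean less, by −3.5 to −5%, −7 to −11% and −7 to −15%. The geometric CV is another matter:
- True CV 40%: dropping gives 33 / 29 / 25%, and LLOQ/2 gives 52 / 58 / 59%, which is further off at every share.
- True CV 60%: dropping gives 50 / 42 / 37%, and LLOQ/2 gives 70 / 75 / 72%.

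**Part 3: pre-dose zero on Day 14.** With a rising first interval the linear rule applies. Replacing a quantifiable pre-dose value by 0 then removes 0.5 × t1 × Ctrough from AUCtau, where t1 is the first post-dose sampling time. Since AUCtau = tau × Caver, the relative loss is 0.5 × t1 × (Ctrough/Caver)/tau. Assume Ctrough/Caver of 0.1–0.5, t1 of 0.5–2 h, and tau of 12 or 24 h.
- Smallest loss: 0.5 × 0.5 × 0.1/24 = 0.1%.
- Largest loss: 0.5 × 2 × 0.5/12 = 4.2%.

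The AUC accumulation ratio, which divides the last-dose AUCtau by the first-dose AUCtau, falls by the same percentage. If the zero were also carried into Ctrough or Cmin, the planned geometric mean could not be computed, because the logarithm of zero does not exist.

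**The case against.** The strongest reply is that this is loose wording in a descriptive analysis. No PK test is planned, AUC0-t is unaffected by trailing below-LLOQ values, all concentrations are listed, the number of measurements is reported, and handling is to be documented and footnoted. All of that is true and limits the weight. But disclosure neither chooses between two rules nor corrects a summary computed without its lowest values, and the planned median is affected as well.

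Several stronger readings are tempting, and the SAP does not support them.

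- *Sections 5.3.2 and 5.6 flatly contradict each other on a Day 14 pre-dose below-LLOQ sample.* They conflict (missing against zero) only if the first observed concentration is counted per subject over the whole study. Counted per profile, both sections say zero. The SAP does not say which is meant.
- *Day 14 troughs will be reported as zero.* The pre-dose sentence concerns the NCA, and Ctrough and Cmin are read from the plotted concentrations. The zero need not overwrite an observed trough, although nothing rules it out.
- *The SAP explicitly drops below-LLOQ values from the summary tables.* Section 5.3.2 names the PK analysis and plots. Its reach to the Ctrough and Cmin tables is an inference, drawn because the SAP states no other rule.
- *The primary-endpoint summaries are inflated by some known amount.* Nothing in the SAP suggests any particular share below LLOQ, and the share may be nil.

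For part 1, one can read the early zero as the specific rule that overrides the general NQ sentence, or NQ as meaning samples that could not be assayed. Either is plausible, but the SAP states neither, and its own labelling goes against the second.

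**Conclusion.** The point holds at minor to moderate weight. Three things stand on the text: the double rule for early samples, an exclusion of later values that reaches beyond AUC and lambda-z at least to the plots, and a pre-dose zero with no Day 1 limit. The upward bias in mean profiles is a certain consequence of the rule whenever some but not all subjects are below LLOQ. For the Ctrough and Cmin group summaries it follows by inference.

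The size is conditional. The range of 8–57% for the geometric mean and 5–45% for the median belongs to an assumed 10–40% below LLOQ and CV 40–80%, and falls to nothing if every later sample is quantifiable. The literal Day 14 zero costs AUCtau at most about 4% on the assumed inputs. It matters more if it is carried into Ctrough or Cmin. A reader might infer that the PK conclusions as a whole are unsafe, and the SAP does not support that: AUC0-t is not touched by trailing below-LLOQ values and no inference is planned on PK.

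**What to change.** Amend SAP sections 5.3.2 and 5.6 as follows.

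- **Pre-dose zero:** limit it to the sample before the first dose on Day 1, use Day 14 pre-dose values as measured, and state that zeros are never carried into Ctrough or Cmin.
- **Early samples:** keep zero for Day 1 below-LLOQ samples before the first quantifiable concentration, in both the NCA and the mean profiles, and say that the phrase about the first observed concentration refers to Day 1.
- **NQ sentence:** limit it to samples with no assay result.
- **Later samples:** limit the exclusion to AUC and lambda-z. For Ctrough, Cmin, time-point summaries and PK/PD plots, keep below-LLOQ values in n, report their number per group and time point, and give the median and range with these values ranked lowest and displayed as below LLOQ.
- **Means:** if a mean is shown while below-LLOQ values are present, state one handling rule in advance and put the count beside it. LLOQ/2 should not be described as less biased overall. It reduces the error in the geometric mean but can worsen the geometric CV.

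The cost is SAP wording and minor programming. The downside is that some low-dose summaries will become lower or will be shown as below LLOQ instead of as a number.

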2.3 Exploratory Objectives

2.4 Primary endpoints

- Linaprazan glurate and linaprazan PK parameters after single and repeated administration of linaprazan glurate (when applicable):
 - $\circ~$ Area under the plasma concentration vs. time curve (AUC) at different timepoints: AUC_{0-24}, AUC_{0-12}, AUC_{12-24}, AUC_{24-48}, and AUC_{0-t}.
 - The minimum, end-of dosing interval, maximum and average plasma concentrations C_{trough}, C_{max}, C_{aver}.

Statistical Analysis Plan CX842A2107 Version 2.0, 04-Oct-2023

- Percentage of time gastric pH >4 at Day 1 and Day 14, over a 24-hour monitoring period following linaprazan glurate administration.

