3.1 Study Design

This is a Phase I, single-center, open parallel-group, randomized study designed to evaluate the PK, PD, safety, and tolerability of single and repeated oral doses of linaprazan glurate at three dose levels in healthy male and female subjects.

An overview of the study design is shown in

Figure **1**. The overall schedule of events is presented in Appendix Table 1. The detailed schedule of events for individual visits are tabulated in the CSP (see Tables 8.1-2 to 8.1-7 of the CSP for details).

Subjects will be randomized into 1 of 6 dose groups. There will be 6 dose groups as follows:

- No 1: 25 mg linaprazan glurate (1x25 mg oral tablet) QD for 14 days
- No 2: 50 mg linaprazan glurate (2x25 mg oral tablet) QD for 14 days
- No 3: 75 mg linaprazan glurate (3x25 mg oral tablets) QD for 14 days

- No 4: 25 mg linaprazan glurate (1x25 mg oral tablet) BID for 14 days
- No 5: 50 mg linaprazan glurate (2x25 mg oral tablet) BID for 14 days
- No 6: 75 mg linaprazan glurate (3x25 mg oral tablets) BID for 14 days

Subjects participating in the study will attend 7 visits to the clinical research unit (CRU): a screening visit (Visit 1) followed by 6 visits (Visit 2-7). Visit 2, Visit 5 and Visit 7 are residential stays at the CRU and Visit 3, Visit 4, and Visit 6 are outpatient visits. The participants will also be followed by a remote follow-up/end-of-study visit via telephone (Visit 8), 7 days (±2 days) after the final dose.

Figure 1. Overview of study design

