4.6.1 Primary and secondary analyses

PK parameters:

When applicable, the following PK parameters will be obtained or calculated from the plasma concentration-time data of linaprazan glurate and linaprazan after QD or BID dosing with linaprazan glurate:

- AUC_{inf} (the area under the concentration-time curve from time zero extrapolated to infinity)
- AUC_{extrap%} (% extrapolated AUC)
- AUC_{0-t} (area under the concentration-time curve from time zero to t=last)
- Partial AUC (area under the concentration-time curve from time zero to t=12h and 24h, from 12h to 24h, and from 24h to 48h)
- C_{max} (maximum observed concentration)
- C_{min} (minimum observed concentration)
- C_{trough} (Concentration before next dose)
- C_{aver} (average concentration in a 12 or 24 h dose interval)
- T_{max} (time to maximum observed concentration)
- T_{1/2} (terminal half-life)
- CL/F (apparent total clearance)
- V/F (apparent volume of distribution)
- R_{acc} (accumulation ratio for C_{max} and AUC in a 12 or 24 h dose interval)

Additional PK parameters may be determined, such as:

- λ_z (elimination rate constant)
- T_{lag} (Delay between the time of dosing and the time of appearance of plasma concentration)
- AUC_{tau} (the area under the concentration-time curve in a dosing interval)

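### The <LLOQ rule has no provision for samples between two BID doses; under one reading of the SAP it can substantially inflate BID AUC0-12 and AUC0-24, and it conflicts with the pre-dose rule in section 5.6

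*SAP*

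**What the plan says.** Section 5.3.2 has two rules for <LLOQ results. Early ones: "values <LLOQ before the first observed concentration will be entered as zero". All others: "values <LLOQ at any other time point will be excluded from the analysis (i.e., handled as missing data". It adds that the handling will be justified and documented.

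Section 5.6 calculates areas by linear up / log down: "linear trapezoidal rule is used when concentration data is increasing and the logarithmic trapezoidal rule is used when concentration data is decreasing". It also says: "Pre-dose concentration values will be excluded from the NCA and set to 0". It does not say whether this covers the pre-dose sample of the second dose on a BID day.

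The partial areas in section 4.6.1 are "area under the concentration-time curve from time zero to t=12h and 24h, from 12h to 24h, and from 24h to 48h". Section 2.4 makes them primary endpoints for both linaprazan glurate and linaprazan. Three of the six groups in section 3.1 are BID (for example "No 4: 25 mg linaprazan glurate (1x25 mg oral tablet) BID for 14 days"), so a second dose falls inside the 0-24 h window and at the boundary between AUC0-12 and AUC12-24. The SAP does not say whether a BID day is run as one profile or split at each dose.

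**The concern.** Deleting <LLOQ values is largely harmless in the tail of a single-dose profile, because nothing follows them. On a BID day something does follow. A <LLOQ sample late in the first interval comes after the first measurable concentration, so section 5.3.2 deletes it. The next retained value may then be close to the peak after the second dose. That value is higher than the last one retained, so the linear rule joins them across hours when the analyte was unmeasurable. The concentration interpolated at 12 h, where AUC0-12 ends, is falsely high as well.

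A QD day has no second dose in the window and cannot form this bridge. The artefact would therefore push areas up in one regimen only, under a primary objective that covers both. For BID, the area over a dosing interval also feeds Caver, CL/F, V/F and Racc (section 5.6).

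**Working it through.** The SAP states no figure on this point, so there is nothing to reproduce. The check asks how large the effect is if it occurs, and when it does not occur.

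**Inputs from the SAP:** the two <LLOQ rules (5.3.2), linear up / log down and the pre-dose rule (5.6), the AUC windows (4.6.1), the BID groups (3.1).

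**Assumptions, because the SAP gives no values:** one compartment, ka = 2 per h; samples at 0, 0.5, 1, 1.5, 2, 3, 4, 6, 8, 10 and 12 h after each dose; LLOQ 1 to 5% of Cmax; half-life 1 to 3 h. Sampling times are left to the protocol (section 4.6).

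**Model:** C(t) = [ka/(ka − k)] × (exp(−kt) − exp(−ka·t)), with k = ln 2 / half-life, and the same curve added from 12 h for the second dose.

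**Worked case: half-life 1 h, LLOQ 5% of Cmax.** Concentrations in % of Cmax: 17.05 at 4 h, 4.28 at 6 h, 1.07 at 8 h, 0.27 at 10 h, 0.07 at 12 h, 93.07 at 12.5 h. The 6 to 12 h samples are deleted.

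- Interpolated value at 12 h: 17.05 + (8/8.5) × (93.07 − 17.05) = 88.6, against a true 0.07.
- Area 4-12 h: (17.05 + 88.6)/2 × 8 = 422.6. The full profile gives 249.64 − 225.08 = 24.56.
- AUC0-12: (225.08 + 422.6)/249.64 = 2.59, an inflation of 159%.
- With <LLOQ entered as zero: (225.08 + 17.05/2 × 2)/249.64 = 0.97.

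**BID inflation relative to the full sampled profile** (one continuous profile, no zero set at 12 h, LLOQ 1 to 5% of Cmax):

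| Half-life | AUC0-12 | AUC0-24 |
|---|---|---|
| 1 h | 67 to 159% | 37 to 79% |
| 1.5 h | 21 to 78% | 13 to 41% |
| 2 h | 0 to 17% | 0 to 9% |
| 3 h | 0% | 0% |

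The upper ends at 1.5 h are fragile. The 8 h concentration is almost exactly 5% of Cmax. If that sample is kept, the maxima are 48% and 25%; if it is deleted, they are 78% and 41%.

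**Comparators on the same assumptions.** QD AUC0-12 under section 5.3.2: ratio 0.90 to 1.00, never inflated. BID with <LLOQ entered as zero: 0.96 to 1.00. BID with the <LLOQ sample at 12 h set to zero under section 5.6: AUC0-24 0.99 to 1.04, AUC0-12 at most 1.18.

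**Wider grid, ratios to the exact area** (half-life 0.5 to 8 h; LLOQ 0.1, 1 and 5% of Cmax; sparse sampling at 0, 1, 2, 4 and 8 h after each dose, plus 12 and 24 h). These ratios include the trapezoid's own sampling error.

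| BID handling, 12 h sample <LLOQ | AUC0-12 dense | AUC0-12 sparse | AUC0-24 dense | AUC0-24 sparse |
|---|---|---|---|---|
| Deleted (5.3.2) | 1.15 to 3.71 | 1.34 to 4.04 | 1.07 to 2.37 | 1.16 to 2.44 |
| 12 h set to 0 (5.6) | 0.93 to 1.15 | 0.80 to 1.59 | 0.93 to 1.02 | 0.77 to 1.09 |
| All <LLOQ as zero | 0.92 to 0.98 | 0.77 to 0.93 | 0.92 to 0.98 | 0.77 to 0.93 |

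Inflation appears only at half-lives up to about 1 h (LLOQ 0.1%), 1.5 h (1%) or 2 h (5%).

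**Cost of zeroing a quantifiable trough.** At a half-life of 8 h and LLOQ 1%, setting the 12 h value to zero lowers the AUC0-12 ratio from 0.99 to 0.94 (dense) or from 0.98 to 0.88 (sparse).

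**The case against.** The strongest reply is that the effect is conditional. It needs three things together: the 12 h sample is <LLOQ, both doses are run as one profile, and the section 5.6 pre-dose rule is not applied at 12 h. The SAP establishes none of them, and nothing in it places either analyte in the affected half-life range. This stands. A reader might infer that the rule does inflate AUC in the BID groups; the document supports only that it can.

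The SAP also thinks in dosing intervals: Caver, Racc and AUCtau are all defined that way. If each dose is a separate profile, a <LLOQ sample at 12 h precedes the first measurable value of its own interval, becomes zero, and no bridge forms. That is a reasonable reading, but the SAP does not adopt it.

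The pre-dose rule in section 5.6 would cut most of the bridge. This also stands, within limits. For a <LLOQ sample at 12 h, section 5.3.2 says missing and section 5.6 says zero. The latter, applied literally, discards measured troughs too, and with sparse sampling it can leave a sizeable AUC0-12 error.

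The promise to justify and document the handling is no substitute for a fixed rule on a primary endpoint.

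Finally, PK results are summarised descriptively, and the SAP plans no QD-versus-BID test of AUC. QD is an evening dose, while the BID pH windows start from the morning dose. A reader might expect Day 1 AUC0-12 to agree between 25 mg QD and 25 mg BID, but dosing time already separates them. This limits the harm to distorted estimates.

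**Conclusion.** The concern holds in conditional form. As written, section 5.3.2 deletes <LLOQ values between two doses, and with linear-up this can inflate BID AUC0-12 by about 20 to 160% and AUC0-24 by about 13 to 80% for assumed half-lives of 1 to 1.5 h. The effect is zero at 3 h or longer under those assumptions, and whenever the 12 h sample is quantifiable. It may touch one analyte and not the other. All sizes rest on assumed kinetics, LLOQ and sampling times and are not estimates for this trial.

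The conflict between sections 5.3.2 and 5.6 for a <LLOQ sample at 12 h does not depend on those assumptions wherever the pre-dose rule is taken to reach the second dose. The sections leave more than one defensible value for a primary endpoint.

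A reader might extend the point to AUC24-48 in subjects who fall below LLOQ before 48 h. That was not quantified, is not specific to BID, and is not part of this conclusion.

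**What to change.** Amend sections 5.3.2 and 5.6 to state that:

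- the <LLOQ rule applies within each dosing interval;
- for BID, AUC0-12 and AUC12-24 are calculated as separate intervals, and AUC0-24 is their sum;
- <LLOQ samples after the last quantifiable value of an interval, up to and including the next pre-dose sample, enter area calculations as zero and are left out of the lambda_z regression;
- the pre-dose rule in section 5.6 is limited so that it agrees with section 5.3.2 and a quantifiable trough at 12 h keeps its measured value.

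The cost is a few lines of SAP text and the matching NCA set-up. Zero entry is one convention among several and has a downward bias: up to about 4% relative to the full sampled profile under the dense schedule for half-lives of 1 to 3 h, and more if sampling is sparse. That is small beside the inflation it prevents.
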